4.3.4 Post Study Follow up and Procedures

Subjects will be followed up by the Allergist in the clinical service and the monitoring and treatment of adverse events will be done during regular outpatient visits with the allergy team.

4.4 Discontinuation/Withdrawal

4.4.1 Discontinuation Criteria

Subjects will be free to withdraw from the study at any time without affecting their future medical care.

The safety of study participants is paramount: subjects who are assessed as having anaphylaxis to OIT dose at home but who have not administered IM adrenaline as per the management plan will have further updosing suspended until the family undergo retraining on the recognition and management of allergic symptoms.

A participant may be withdrawn from the study under the following circumstances:

- If, in the opinion of the study team, compliance with study procedures is suboptimal such that it compromises the patient's safety.
- If, in the opinion of the study team, further participation would adversely affect the participant's health.
- A child develops an exclusion criteria during the updosing phase of the study e.g. a new medication (which would normally be a contra-indication) is commenced.
- If consent is withdrawn or the subject fails to return for a study visit.

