4.3 Study Visits and Procedures Overview

There will be 9-10 hospital visits for the BET group, 10-11 hospital visits for the BER group over the entire study duration. There will be 2 hospital visits for the control group.

[figure not shown]

Figure 2: POET Study Timeline

Study Timepoints	TS	T0	T1C		T1P/ T2P		T3	T4
	Screening & Cooked Egg FC	Baked Egg FC	Cookie Initial Escalation	Home Cookie Build-up	Pancake Initial Escalation	Hospital Pancake Build-up	Exit Cooked Egg FC	SU FC
Informed consent	X							
Medical history	X							
Concomitant medications	X	X	X		X	X	X	X
Adverse events		X	X	X	X	X	X	X
Physical exam	X	X	X		X	X	X	X
Spirometry		(X)					(X)	
Asthma control test	X	(X)					(X)	
SCORAD	X							
POEM	X							
Skin Prick Test	X*						X	X
Blood test	X*						X	X
HRQL Assessments	X		X		X		X	X

Table 1: Study Procedures

(X) may be performed, depending on clinical need; X* - Results from SPT/ IgE performed within 3 months prior will be used and need not be repeated

X are procedures applicable to control subjects

FC – Food Challenge; SU – Sustained Unresponsiveness

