4.4.2 Discontinuation Visit and Procedures

All subjects withdrawn from study will be given appropriate care under medical supervision until the symptoms of any adverse event resolve or the subject's condition becomes stable. Subjects withdrawn from study will be invited to a final discontinuation visit and if willing, the following will take place:

- Skin prick test (SPT) to commercial extracts of egg.
- Blood test - Serum IgE to egg white, ovomucoid and ovalbumin and immunoprofiling tests (4.3.2.10)
- Health-related quality of life (HRQL) assessment (4.3.2.9)

Withdrawn subjects will be offered continued follow up in the Allergy clinical service as per current clinical practice.

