6.4 Specific Restrictions / Requirements

Subjects in the control arm will be advised strict egg avoidance including all baked egg products. However for those who were already previously tolerating baked egg products, they will be allowed to continue consumption of baked egg products outside of study, up to a maximum of 2.5g baked egg protein (approximately equivalent to a slice of cake or one muffin) per week.

Subjects in the BER group undergoing cookie OIT will be counselled for strict egg avoidance including all baked egg products outside of the study treatment. Subjects in the BET group who had tolerated baked egg products prior to study will be allowed to continue the consumption of baked egg products outside of study, up to a maximum of 2.5g baked egg protein (approximately equivalent to a slice of cake or one muffin) per week. This limit is placed because baked egg consumption in BET subjects may enhance desensitisation to cooked egg, and subjects taking larger quantities of baked egg outside of pancake OIT may have better rates of desensitisation. However, as pancake OIT outcomes should be assessed

in a real-world setting, this will include allowing baked egg consumption in egg allergic children who are already tolerating baked egg.

Subjects who are receiving anti-IgE therapy, oral immunosuppressants, beta-blocker, ACE inhibitor or immunotherapy for other allergens will fall under the study's exclusion criteria and be withdrawn from study.

Subjects will be advised to avoid intense physical exercise up to 2 hours before and after each OIT dose intake.

6.5 **Blinding**

This is an open label study. Blinding will not be performed.

6.6 **Concomitant therapy**

Participants may continue usual medications, including those taken for asthma, rhinitis, and eczema during the study. Antihistamines must not be taken on the day of updosing and must be stopped prior to FC visits as per Section 4.3.2.8. Participants (or their parents) will be asked to document any use of medication (including rescue medication) in home diary cards.

All medications (prescription and over the counter) taken by the participant should be documented.

7 **SAFETY MEASUREMENTS**

7.1 **Definitions**

An adverse event (AE) is any untoward medical occurrence in a patient or clinical investigation subject administered a pharmaceutical product and which does not necessarily have a causal relationship with this treatment.

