- There is insufficient or incomplete evidence to make a clinical judgement of the causal relationship.

7.3 Collecting, Recording and Reporting of Adverse Events and Serious Adverse Events to CIRB

All adverse events will be recorded on a subject's diary from the time the participant provides consent until the time the event resolves or until 30 days after the participant completes study treatment. Adverse events may be discovered through observing and questioning the participant or receiving an unsolicited complaint and questioning the participant in an objective manner. All adverse events will be recorded, regardless of their severity or relation to study medication or procedures.

Reporting of adverse events involves the PI submitting to the approving CIRB the completed SAE Reporting Form within the stipulated timeframe. PI is responsible for informing the institution representative (local SAE resulting in death), sponsor or regulatory bodies as required and appropriate.

Reporting timeline to CIRB:

- SAE that result in death, regardless of causality, should be reported immediately - within 24 hours of the PI becoming aware of the event.
- All "related" SAE (definitely / probably / possibly) irrespective of severity or expectedness, need to be reported to CIRB within 24 hours of the PI becoming aware of the event.

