9.2 Statistical and Analytical Plans

The primary analysis will be performed on an intention to treat basis: all subjects allocated to each arm will be analysed together as representing that treatment arm, irrespective of compliance and whether or not they have completed the prescribed regimen. A secondary

analysis will also be performed on a per protocol basis. Statistical analysis was performed using SAS software version 9.4 for Windows (Cary, NC: SAS Institute Inc.). Statistical significant is set at $p < 0.05$.

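### Study withdrawal is not separated from stopping OIT and may follow a single missed visit, so T3 outcomes can go missing mainly in the active arm and some safety data are at risk

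*Combined protocol and SAP*

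**What the plan says.** Section 4.4.1 opens its list with "A participant may be withdrawn from the study under the following circumstances". The grounds are:

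- "compliance with study procedures is suboptimal such that it compromises the patient's safety";
- harm to the child's health from continuing, in the team's opinion;
- a new exclusion criterion arising during updosing;
- "If consent is withdrawn or the subject fails to return for a study visit".

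The only lesser step in 4.4.1 is suspension of updosing while a family is retrained. Section 6.4 is firmer: children on prohibited therapies fall under the "exclusion criteria and be withdrawn from study".

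Section 4.4.2 then states: "Subjects withdrawn from study will be invited to a final discontinuation visit and if willing, the following will take place". What follows is a skin prick test, blood tests and the quality-of-life questionnaire. Table 1, by contrast, marks adverse events and concomitant medication at T0 and at each later hospital visit.

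Section 4.3 gives 9–10 hospital visits for baked-egg-tolerant and 10–11 for baked-egg-reactive active children. For the other arm it says: "There will be 2 hospital visits for the control group". Section 4.3.2.6 gives T3 to active children with 16 weeks or more of maintenance, and to all controls.

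Section 9.2 analyses every allocated child "irrespective of compliance and whether or not they have completed the prescribed regimen". It has no rule for a missing T3 result, and 3.5 rules out replacement.

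**The concern.** The analysis in 9.2 needs a T3 result from every randomised child, including those who stop OIT. Section 4.4 gives stopping OIT and leaving the study a single exit and describes no status of being off OIT but still followed. The T3 eligibility wording reinforces this for active children only.

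The imbalance comes from the design. Updosing exists only in the active arm, and that arm has many more visits to miss. Two of the grounds rest on the opinion of a team that knows the allocation. Differential missingness in the primary outcome is then possible, and in a trial of 33 each lost result matters.

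Safety is the second issue. The diary holds the home doses and reactions (4.3.2.5), yet the exit visit does not ask for it. Section 7.3 runs adverse event recording "from the time the participant provides consent until the time the event resolves or until 30 days after the participant completes study treatment". That end point is hard to apply to a child who never completes treatment.

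**Working it through.** **1. Visits that can be missed after allocation.** The stated totals are 9–11 (active) and 2 (control). TS precedes randomisation in both arms. T4 exists only in the active arm and follows the primary endpoint.

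- Active: 9 − 2 = 7 to 11 − 2 = 9 visits.
- Control: 2 − 1 = 1 visit.

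These are approximate: T0 can be waived after a recent failed baked egg challenge, and repeated updosings add visits.

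**2. Chance of meeting the missed-visit ground.** The documents give no miss rate. I assume the same independent rate *q* per visit in both arms and compute 1 − (1 − *q*)^*k*.

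| *q* | Control, *k* = 1 | Active, *k* = 7 | Active, *k* = 9 |
|---|---|---|---|
| 2% | 2.0% | 1 − 0.98^7 = 13.2% | 1 − 0.98^9 = 16.6% |
| 5% | 5.0% | 1 − 0.95^7 = 30.2% | 1 − 0.95^9 = 37.0% |

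In children, this is 22 × 0.132 = 2.9 to 22 × 0.370 = 8.1 active, against 11 × 0.02 = 0.2 to 11 × 0.05 = 0.6 control. Counting all stated visits instead gives 16.6–19.9% against 4.0% at 2%, and 37.0–43.1% against 9.8% at 5%. Those levels are too high for the period that matters, although the relative gap is smaller.

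**3. The plan's own attrition.** Section 9.1 allows 30%, not split by arm. The stated 33 reproduces with an unpooled two-sided Z test:

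- controls: (0.15 × 0.85 + 0.65 × 0.35 / 2) × (1.960 + 0.842)² / 0.50² = 7.57;
- total: 3 × 7.57 = 22.7;
- with attrition: 22.7 / 0.70 = 32.5, so 33.

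If the 30% applies equally to the active arm, 22 × 0.30 = 6.6, or about 6–7 active children.

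**4. What missing T3 results could do.** This illustration uses the plan's 65% and 15%, Fisher's exact test and loss unrelated to outcome. The treatment of missing results is my assumption, since 9.2 states none.

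- All 22 and 11 observed: power 75.4%.
- 30% lost in the active arm only, missing counted as failure: the active rate becomes 0.65 × 0.70 = 45.5%, power 32.1%.
- 30% lost in both arms, missing counted as failure: 45.5% against 0.15 × 0.70 = 10.5%, power 44.4%.
- Active losses simply dropped (15 against 11): power 67.9%.

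The result depends heavily on how many T3 results are missing and how they are handled.

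**5. Exit visit against scheduled visits.**

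| Item | Table 1, T3 | 4.4.2 exit visit |
|---|---|---|
| Skin prick test, blood, quality of life | yes | yes, if willing |
| Adverse events | yes | not named |
| Concomitant medication | yes | not named |
| Cooked egg challenge | yes | not named |

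Diary return is not named at the exit visit either.

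**The case against.** The strongest reply is that the plan permits this loss without requiring it. The lead-in to 4.4.1 says *may*, and the missed-visit ground shares a bullet with withdrawn consent, so it can be read as loss to follow-up. Visit timing is flexible (updosing at 4 weeks, minimum 3; T3 anywhere from 12 to 18 months), so a missed date can be rebooked. All of that stands. A reader might infer that data are lost by rule; only the 6.4 ground is worded as mandatory.

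A reader might also infer that ordinary poor adherence leads to withdrawal. It does not: the ground applies only where safety is compromised, and 6.3.2 to 6.3.4 handle missed doses, illness and refusal by adjusting the dose.

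On safety, 7.3 requires all adverse events to be recorded, 7.5 monitors from enrolment to study completion, and 6.6 requires all medication to be documented. Section 4.3.2.5 tells families to report any symptoms. So the inference that OIT reactions will be understated goes beyond the text. What remains is the period since last contact, an uncollected diary, and a 7.3 end point that is unclear for early stoppers. The care promised in 4.4.2 until events resolve is clinical care and not stated as data collection.

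Finally, 9.2 defines who is analysed, and 4.4.1 removes nobody from that set, so there is no direct contradiction. The difficulty is practical: the set is complete while its outcomes may not be.

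**Conclusion.** The point holds as a design weakness. The plan permits study withdrawal for one missed visit and for treatment-related reasons, requires it for prohibited therapy, and describes no route to T3 for an active child who has stopped OIT. Every control has that route.

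Exposure to the missed-visit ground is about 13–37% of active children against 2–5% of controls. This rests on an assumed, equal and independent 2–5% miss rate and on about 7–9 visits against 1. It does not predict withdrawals, because the ground is discretionary. The 12.5–36% early discontinuation for adverse events that 6.1 cites for egg OIT suggests that stopping will not be rare, but it does not measure missed visits.

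The main consequence is primary outcomes missing differentially in an open-label trial. Safety data are at risk to a smaller degree; the documents do not show that they will be lost.

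**What to change.** Without changing who stops OIT or when:

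- **4.4.1:** state that stopping OIT does not end study participation and that only withdrawal of consent ends follow-up. Delete failure to return for a visit as a ground for study withdrawal.
- **6.4:** reconcile the mandatory study-withdrawal wording with this.
- **4.3.2.6:** reconcile the T3 eligibility wording, so that active children off OIT are invited to the T3 assessments in the same 12–18 month window as controls. This applies where the family agrees and the team judges the challenge suitable under 4.3.2.8.
- **4.4.2:** add adverse events since last contact, concomitant medication, diary return and the reason for stopping, by phone if the family will not attend.
- **7.3:** say how the adverse event window ends for a child who stops early.

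The cost is amendment wording, plus a call or a T3 visit for a few children: about 6–7 of 22 if the 30% attrition falls equally on the active arm. The T3 visit is a real addition for these children, because the current wording does not schedule one.

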4.4.2 Discontinuation Visit and Procedures

All subjects withdrawn from study will be given appropriate care under medical supervision until the symptoms of any adverse event resolve or the subject's condition becomes stable. Subjects withdrawn from study will be invited to a final discontinuation visit and if willing, the following will take place:

- Skin prick test (SPT) to commercial extracts of egg.
- Blood test - Serum IgE to egg white, ovomucoid and ovalbumin and immunoprofiling tests (4.3.2.10)
- Health-related quality of life (HRQL) assessment (4.3.2.9)

Withdrawn subjects will be offered continued follow up in the Allergy clinical service as per current clinical practice.

5.1 Trial Product (s)

5.1.1 Pancake & Cookie Recipes – A set of standardised baking tools including baking tray, measuring cup, measuring spoons, digital weighing scale, frying pan, syringes will be provided to subjects in the active arm, to ensure uniformity in the cookies and pancake.

Pancake Recipe

Recipe A		Makes	Amount of pancake to be consumed	Egg protein (mg)
Plain Flour	55g	6 pancakes (30ml or 1/8 cup per pancake)	1/32	37.5
Baking Powder	1 tsp		1/16	75
Baking Soda	1/8 tsp		1/8	150
Salt	1/8 tsp		¼	300
Sugar	15g		½	625
Butter	15g		1	1250
Recipe B		Makes	Amount of pancake to be consumed	Egg protein (mg)
Plain Flour	110g	6 pancakes (60ml or ¼ cup per pancake)	1	2500
Baking Powder	2 tsp			
Baking Soda	¼ tsp			
Salt	¼ tsp			
Sugar	30g			
Butter	30g			
Milk	120ml			
Egg (65g)	2			
Vanilla Essence	1 tsp			

Method

1. Microwave the butter for 20-30 seconds to melt it.
2. Combine the flour, baking powder, baking soda, salt and sugar in a large-sized bowl. Make a well in the centre and add the cooled melted butter, milk, egg(s) and vanilla essence.
3. Use a wire whisk and mix the wet and dry ingredients together until smooth. The batter should be thick and creamy in consistency.
4. Set the batter aside and allow to rest while heating up your pan.
5. Heat the non-stick pan over medium heat for 2 minutes then turn heat down to **low**.
6. Pour 30ml of Recipe A or 60ml of Recipe B onto the pan.
7. Cook for 3 minutes. Bubbles should appear on the surface and the edge of the pancake should peel off easily to reveal a golden underside.
8. Flip with a spatula and cook for another 3 minutes.
9. Repeat with remaining batter to make a total of 6 pancakes.

*tsp = teaspoon

Cookie Recipe

	Amount of egg used	Makes	Amount of cookies to be consumed daily	Egg protein (mg)
150g Plain Flour 100g Sugar 100g Butter/ Milk-free margarine ½ tsp Baking soda	Recipe C			
	1ml	100 cookies	1	1.25
			2	2.5
			4	5
	Recipe D			
	10ml	100 cookies	1	12.5
			3	37.5
	Recipe E			
	1 whole (65g)	100 cookies	1	75
			2	150
			4	300
	Amount of egg used	Makes	Amount of cookies to be consumed daily	Egg protein (mg)
100g Plain Flour 50g Sugar 50g Butter/ Milk-free margarine ¼ tsp Baking soda	Recipe F			
	2 whole (65g each)	24 cookies	1	625
			2	1250
			4	2500

Method

1. Preheat oven to **180°C**. Microwave the butter or milk-free margarine for 30-40 seconds to melt it.
2. Using a whisk, beat the melted butter with sugar until creamy. Add the egg and continue beating until just incorporated. Avoid beating the egg for too long as cookies will be stiff.
3. Add the flour and baking soda. Mix well together into a dough.
4. Line the square baking tray with baking paper. Roll the dough evenly onto the baking tray.
5. Bake in the oven for 15 minutes at **180°C**.
6. Once out of the oven, immediately cut into 10x10 squares (Recipe C-E) or 6x4 rectangles (Recipe F) before the cookies cool.

5.1.2 Food Safety

Raw Ingredients

- Eggs
 - *Salmonella* bacteria can be present on egg shells and the interior of normal-looking eggs.
 - Proper handling of eggs reduces the risk of *Salmonella* contamination. This includes storing eggs in the refrigerator until they are needed, and ensuring adequate personal hygiene and cleanliness of utensils during food preparation.

Cookies and Pancakes

- Baked and cooked products are subject to microbiological spoilage. This is influenced by factors such as storage temperature, relative humidity, initial contamination and moisture content of the product.
- Water activity, a_w , which is an indicator of moisture content, allows recognition of the spoilage and safety potential of baked goods. Cookies have a low moisture content ($a_w < 0.6$) while pancakes have a high moisture content ($a_w > 0.85$).
- Low moisture baked products such as cookies are less likely to be affected by microbiological spoilage. In high moisture cooked products like pancakes, almost all bacteria, yeasts and moulds are capable of growth.
- To control microbiological spoilage, the following strategies should be taken:
 - Cookies and pancakes should be cooled completely prior to storage.
 - Stored in airtight container.
 - Store at room temperature (if consumed within 2 weeks for cookies, and within 2 hours for pancakes) or in the freezer to prolong storage life.

5.2 Storage and Drug Accountability

Storage Requirements and Stability (Temperature, Duration)

Shelf Stable Ingredients

	Shelf (unopened)	Shelf (opened)
Plain flour	Use by date	6 months*
Sugar	Use by date	18 – 24 months
Oil	Use by date	3 – 5 months
Baking powder	Use by date	3 – 6 months

* Opened flour packets should be stored in air-tight containers.

Perishable ingredients

	Refrigerator
Eggs, in shell	3 – 5 weeks OR Use by date
Butter/ Milk-free margarine	1 – 2 months 6 months
Fresh cow's milk	Use by date (unopened) 3 days (opened)

Baked Products

	Room Temperature (~25°C)	Refrigerator (0 – 4°C)	Freezer
Cookies	2-3 weeks	2 months	8-12 months
Pancakes	2 hours	2 – 3 days	2 months

- Pancake batter must be cooked within 2 hours upon preparation.
- General safe food preparation and handling practices apply.

6 TREATMENT**6.1 Rationale for Selection of Dose**

Current OIT regimens typically involve the daily consumption of an allergen, commencing at a very low dose followed by dose increments over several hours during initial escalation phase and periodically (usually every 2-4 weeks) during build-up phase until the target maintenance dose is achieved (12) This maintenance dose is then continued on a daily basis for months to years. There is considerable variation between studies regarding starting and target maintenance doses.

Egg OIT (using eggs in various forms such as lyophilized egg, dehydrated egg white, pasteurized raw egg white, lightly cooked eggs or hard-boiled eggs) has been reported with much heterogeneity in desensitisation rates ranging from 55% to 100%. Furthermore, the ability of current protocols to induce SU appear to be even more limited (~30%). It is possible that longer duration and higher doses of treatment resulting in higher cumulative dose of allergen may lead to higher rates of allergy remission but this would have to be balanced against the risk of allergic reactions. Safety of egg OIT, just like other OIT, is a concern with early discontinuation due to adverse events reported in 12.5%-36% of children (13).

Only 2 studies have evaluated using baked egg in OIT and both used different doses administered over different durations of time. In the study by Bravin et al, biscuits containing varying amounts of egg protein were administered to baked egg allergic subjects, starting at 125µg and increased daily over 60 days to a target maximum dose of 6.25g after which an open FC to 1 boiled egg was performed to assess for desensitisation. Of the 15 patients recruited, 12 (80%) completed the OIT program and all adverse reactions were mild. The second study by Bird et al. did not report the starting OIT dose but baked egg-allergic subjects underwent an initial escalation phase up to 125mg in hospital followed by home up-dosing to a maintenance dose of 3.8g which was continued for 1 year. This was followed by an open FC to 6g of lightly cooked egg to assess for desensitisation. Again, dosing was well tolerated with only 77 adverse reactions reported of 5605 total recorded doses (1.37% of total doses) and none requiring adrenaline.

Pancakes are expected to be less allergenic than cooked egg because of the wheat matrix but more allergenic than baked egg. In our study, all subjects assessed to be baked egg tolerant will have ingested and tolerated 2.5g of egg protein during the baseline baked egg open FC. BET subjects will hence commence pancake OIT at 37.5mg (1.5% of the 2.5g cumulative dose tolerated during the baked egg FC) with increments every 30minutes to a maximum of 300mg during the initial escalation phase (Table 4). The starting dose of the build-up phase will be 1 step below the dose tolerated during the initial escalation phase to minimise risk of allergic reactions at home, particularly as the presence of co-factors may decrease reaction threshold (see Section 6.4). Dose increments during the build-up phase will occur every 4 weeks (minimum 3 weeks) until a target maintenance dose of 2500mg is achieved (Table 5). Subjects will then remain on the daily maintenance dose for a minimum of 16 weeks or total OIT duration of 18 months, whichever is achieved earlier.

BER subjects who tolerate at least 3mg of muffin will commence OIT with cookies to first desensitise them to baked egg before transitioning to OIT with pancakes. The first dose to be administered during the initial escalation will be individualised based on the outcome of the baseline baked egg FC. Subsequent dose increments during the cookie build-up phase will occur every 2 weeks at home until the target of 2500mg egg protein (the amount tolerated in a baked egg FC) is tolerated. When participants successfully reach the target dose (Table 6 Step 11), they will remain on this dose for a minimum of 2 weeks before undergoing initial escalation with pancake.

All participants who have completed at least 16 weeks of maintenance pancake OIT (Table 5 Step 7) will undergo exit cooked egg FC to assess for desensitisation to cooked egg.

